## **6. GENERAL CONSIDERATIONS FOR DATA ANALYSES AND HANDLING**

### **6.1. General Summary Table and Individual Subject Data Listing Considerations**

Summary tables and listings (e.g., post text tables and individual subject data listings are prepared according to ICH Guideline E3) include a “footer” providing explanatory notes which indicate at a minimum:

1. Date of data extraction.
2. Date of output generation.
3. SAS program name, including the path that generates the output.
4. Any other output specific details that require further elaboration.

Post text tables also include reference(s) to the subject data listing(s) that supports the summary data. The data extraction date links the output to the archived database that is locked to ensure replication of the results.

In general, row entries in post text tables are made only if data exists for at least one subject (e.g., a row with all zeros will not appear). The only exception to this rule applies to tables that summarize the study termination status of subjects (e.g., reasons for not completing the study). In this case, zeros will appear for study termination reasons that no subject satisfied. The summary tables clearly indicate the number of subjects to which the data apply and unknown or not performed are distinguished from missing data.

Summary tables for medications and medical conditions are coded according to standard dictionaries (e.g., WHO Drug standard dictionary). Adverse event preferred terms and body/organ systems are coded using the latest MedDRA dictionary. The MedDRA dictionary can be used, as well, in the coding of signs and symptoms, medical history, physical examination abnormalities, and clinical diagnoses.

Supportive individual Subject Data Listings, at a minimum, are sorted and presented by investigational site (center). Listings also include subject number, visit number, and visit date.

Other subject data listings that do not support a specific summary table are included to provide an enumeration of the investigator’s general comments. This listing is also organized by investigator. Sorting is also performed with respect to subject, reference visit number and date, visit relative day, date of the comment, and the text of the comment.

Imputed or derived data will be flagged in the individual subject data listings. Imputed data are not incorporated into any raw or primary datasets. These data are retained in derived analysis datasets.

## **6.2. General Post Text Summary Table and Individual Subject Data Listing Format Considerations**

The default convention is to number tables and listings using a decimal system to reflect main levels of unique tables and listings and sub-levels of replicate tables and listings with two digits per level (e.g., Table XX.YY.ZZ. ...).

1. The first level number should be consistent with the corresponding CSR appendix in which the tables or listings will appear. For example, the post text tables usually occupy Appendix 14 and the individual subject data listings are put in Appendix 16. All post text tables should have a main number level 14 and listings 16. The subject accounting and disposition table is usually first in the first section of the report and should be numbered Table 14.1. The supportive subject data listing would be Listing 16.1. A subset by sex table would have the number Table 14.1.2, etc.
2. Subject accounting and final disposition should appear as the second level number (Table 14.1 series). Baseline and demographic profile occupy the next sub-level (Table 14.2 series). Efficacy should come next (14.3 series) followed by safety (table 14.4 series). Reasons for subjects' being excluded from efficacy and protocol violation summary tables should appear as the last level (Table 14.5 series). Similar conventions should be applied to the subject data listings.
3. The title should be complete, accurate, and concise. The last line of the title should provide the analysis group being summarized (e.g., Intent-to-Treat Subjects or Per-Protocol Efficacy Subjects). If possible, the units of measurement for data contained in the table can appear in parentheses to conserve space in the body of the table.

Whether in the title or body of a table or listing, units must always be specified for all appropriate data.

4. If possible, variables being summarized and statistics reported should appear in the left most column of a table. In general, the listings should be sorted and presented by investigational site, and subject number. Site can appear in the banner of the listing. From left to right, the subject number, visit number, visit date, and relative day should appear. All tables and listings must have explanatory notes that give, at a minimum, data extraction date, output generation date, complete program name and path where it is stored, CRF pages from which the data were obtained, and supportive listings or tables supported, as appropriate. The definition of all derived variables and decodes for coded data must appear in the notes. Due to space limitations, tables and listings may require a page of notes as a one-time preface to the output.

## **6.3. Data Management**

IBM Clinical Development is the software platform used for Electronic Data Capture (EDC). Derived datasets are created using (SAS®) software. Data analyses and summary tables are generated using SAS version 9.4 or above.

## **6.4. Data Presentation Conventions**

Continuous variables (e.g. age) are summarized using descriptive statistics (the number of subjects with available data, the mean, standard deviation (SD), median and minimum and maximum). Categorical variables (e.g. race) are summarized using counts and percentages. Percentages are calculated using the total subjects in the XADAGO group.

The following conventions are applied to all data presentations and summaries.

- For continuous variables, all mean and median values are formatted to one more decimal place than the measured value. Standard deviation values are formatted to two more decimal places than the measured value. Minimum and maximum values are presented with the same number of decimal places as the measured value.
- For categorical variables, the number and percentage of responses are presented in the form XX (XX.X%) where the percentage is in the parentheses.
- Date variables are formatted as DDMMYY for presentation. Time is formatted in military time as HH:MM for presentation.
- Wherever possible, data will be decimal aligned.
- Unless otherwise stated, any statistical tests performed will use 2-sided tests at the 5% significance level.

The table and listing shells and table of contents as part of this SAP provide the expected layout and titles of the tables, listings and figures. Any changes to format, layout, titles, numbering, or any other minor deviation will not necessitate a revision to the SAP nor will it be considered a deviation from planned analyses. Only true differences in the analysis methods or data handling will necessitate such documentation. The appropriate listings supporting the tables will be included and are not specified in the individual sections throughout the document.

## **6.5. Analysis Populations**

### **6.5.1. Screen Failures**

All subjects will be enrolled into the study. There are no screen failures.

### **6.5.2. Safety Population**

The ‘Safety Population’ is defined as all subjects who sign informed consent for the study, complete baseline assessments, and receive at least 1 dose of XADAGO.

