11.4. Recording Adverse Events

AEs spontaneously reported by the patient and/or in response to an open question from the study personnel or revealed by observation will be recorded during the study at the investigational site.

Information about AEs (and SAEs) will be collected from the time the patient signs the informed consent for this study and takes the first study dose of XADAGO until the patient’s last follow-up visit. The AE term should be reported in standard medical terminology when possible. For each AE, the investigator will evaluate and report the onset date, resolution date, intensity, causality, action taken, serious outcome (if applicable), and whether or not it caused the patient to discontinue the study.

Intensity will be assessed according to the following scale:

- Mild (awareness of sign or symptom, but easily tolerated)
- Moderate (discomfort sufficient to cause interference with normal activities)
- Severe (incapacitating, with inability to perform normal activities)

It is important to distinguish between serious and severe AEs. Severity is a measure of intensity whereas seriousness is defined by the criteria under Section 11.2.2. An AE of severe intensity may not be considered serious.

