12.2. Analysis Populations

The 2 analysis populations are defined in the study's Statistical Analysis Plan (SAP) as follows:

- Safety Population: All patients who sign informed consent for the study, complete baseline assessments, and receive at least 1 dose of XADAGO.
- Evaluable Population: All patients in the safety population who complete at least the MDS-UPDRS assessment at the Study Day 60 visit.

The principal analysis of the primary endpoint will be conducted for the evaluable population. Sensitivity analysis of the primary endpoint will be carried out for the safety population. Safety summaries will be provided for the safety population.

Eligible, consented, and enrolled study participants will be analyzed based on concomitant PD medication regimen change at Baseline:

Cohort A – Patients that have switched to XADAGO from a Dopamine Agonist

Cohort B – Patients that have switched to XADAGO from an MAO-B inhibitor

Cohort C – Patients that are MAO-B inhibitor naïve

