### **9.1. Overall Summary of Tolerability**

The overall summary of tolerability table presents the data for all treated subjects by cohort and overall. Entries in this table are the number of:

1. Subjects treated and subject months of drug exposure by treatment (50 mg vs 100 mg).
2. Subjects with adverse events.
3. Adverse events.
4. Subjects with serious adverse events.
5. Subjects discontinuing due to adverse events.
6. Deaths.

The subject data listing provides a complete disclosure of adverse events as recorded in the CRF and supports this table and all other AE summary table subsets.

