#### **9.2.1. Summaries of Adverse Event Incidence Rates for All Subjects**

The primary presentation of AEs data is prepared without regard to causality or relationship to study medication and classifies events using the most recently available MedDRA dictionary with respect to preferred term and body/organ system for all treated subjects by cohort and overall. Subjects will be counted only once at the body system level and will be counted once for each applicable preferred term; multiple occurrences of the same preferred term for a subject will be counted only once. Subjects who experience more than one event within the same body system are counted once at each preferred term level.

Supplementary tables summarize the events with respect to the maximum severity observed for each preferred term and highest relationship to study medication by cohort and overall. The presentation of adverse events with respect to the severity or intensity of the event usually categorizes the data as mild, moderate, or severe.

The relationship of the event to study medication will be collapsed into two categories, related and not related:

1. Related combines the options possible, probable, and highly probable.
2. Not related is a combination of unlikely and not related.

A by-subject listing of serious adverse event data will be presented.

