### **9.2.3. Summaries of Adverse Incidence Rates for Serious Adverse Events (SAE), Adverse Event Dropouts, and Death**

Adverse event incidence rates, by body system, will be summarized for subjects who report a non-fatal serious adverse event, discontinue treatment prematurely due to an adverse event, and deaths.

A by-subject listing of premature discontinuations due to all causality will be presented.

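### The Safety Population requires completed baseline assessments, which conflicts with how adverse events are collected and with the all-treated set used in SAP section 9

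*SAP*

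**What the plan says.** **Definition.** Protocol 12.2 ("All patients who sign informed consent for the study, complete baseline assessments, and receive at least 1 dose of XADAGO") and SAP 6.5.2 ("all subjects who sign informed consent for the study, complete baseline assessments, and receive at least 1 dose of XADAGO") set the same three conditions for the Safety Population: consent, completed baseline assessments and at least one dose. SAP 6.5.3 defines the ITT population in the same words, so the two sets are identical. The Evaluable Population (Protocol 12.2, SAP 6.5.4) is a subset of the Safety Population and inherits the baseline condition from it.

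**Use.** Protocol 12.2 states: "Safety summaries will be provided for the safety population". The same set serves the sensitivity analysis of the primary endpoint (Protocol 12.2), the demographic table (SAP 7.3) and the medical history table (SAP 7.4).

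**Collection.** Under Protocol 11.4, adverse events are gathered from the time a patient "signs the informed consent for this study and takes the first study dose of XADAGO until" the last follow-up visit. Sections 11.4.1 and 11.4.2 apply the same two triggers, consent and XADAGO taken, to non-serious and serious events. None of these sections mentions baseline completion.

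**Tables.** SAP 9.1, which counts adverse events, SAEs, discontinuations due to adverse events and deaths, says: "The overall summary of tolerability table presents the data for all treated subjects by cohort and overall". SAP 9.2.1 presents incidence "with respect to preferred term and body/organ system for all treated subjects by cohort and overall". SAP 9.2.3 names no population; event rates "will be summarized for subjects who report a non-fatal serious adverse event, discontinue treatment prematurely due to an adverse event, and deaths". On the listing, SAP 9.1 says: "The subject data listing provides a complete disclosure of adverse events as recorded in the CRF".

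**The concern.** Whether a patient finished a rating scale or questionnaire has no bearing on whether that patient was exposed to the drug. With this condition, the Safety Population can be narrower than the set from which events are collected. The protocol sends the safety summaries to the narrower set, while the SAP describes its main safety tables with a different and undefined phrase. A programmer who follows Protocol 12.2 and one who follows SAP 9.1 could produce different denominators for the same table and, if an affected patient has an SAE or dies, different event counts. Single events matter most for exactly these outcomes.

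**Working it through.** The documents give no figure on this point, so there is nothing to reproduce. The check has two parts: a comparison of the text, and an illustration of size on stated assumptions.

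**1. Can a patient be dosed without completed baseline assessments?** Protocol 8.1.1 lists MDS-UPDRS, PDQ-39, MoCA and the Day 1 dose under the Baseline Visit, with the dose last. No sentence there makes the dose wait for finished scales. Protocol 10.1 treats a patient as enrolled once XADAGO is prescribed and consent is given, again without reference to the scales. So the situation is possible. Because everything falls on one visit day, it should be uncommon.

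**2. What happens to that patient in each place?**

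| Place | Set that applies | Dosed patient with incomplete baseline |
|---|---|---|
| Protocol 11.4 to 11.4.2, collection | Consent and XADAGO taken | Events recorded |
| Protocol 12.2, safety summaries | Safety Population | Left out |
| SAP 9.1 and 9.2.1, tables | All treated subjects (undefined) | Counted |
| SAP 9.2.3, SAEs, dropouts, deaths | None named | Not settled |
| SAP 9.1, listing | All events in the CRF | Shown |

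SAP 7.3 uses both the safety population and all treated subjects in one sentence, as if they were the same. SAP 7.1 counts only the Safety and Evaluable sets in the disposition table. The Safety Population is therefore the only defined set a programmer would naturally reach for when building the section 9 tables.

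**3. Size, for illustration only.** From the documents: up to 540 patients (Protocol 8.2, SAP 4.3.1), here all taken as dosed. Assumed, because the documents give neither: a share f of 1% to 5% of dosed patients with incomplete baseline, and a per-patient SAE rate s of 1% to 5% that does not depend on baseline completion.

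- Patients excluded: k = 540 × f, rounded
- Expected SAE patients excluded: k × s
- Chance that at least one SAE patient is excluded: 1 − (1 − s)^k

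| f | k | Left of 540 | Expected SAE patients excluded, s = 1% to 5% | Chance of at least one |
|---|---|---|---|---|
| 1% | 5.4, about 5 | 535 | 0.05 to 0.25 | 5% to 23% |
| 2% | 10.8, about 11 | 529 | 0.11 to 0.55 | 10% to 43% |
| 5% | 27 | 513 | 0.27 to 1.35 | 24% to 75% |

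For example, with k = 27 and s = 5%: 27 × 0.05 = 1.35, and 1 − 0.95^27 = 0.75.

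These losses arise only if the tables are built on the Safety Population as defined. If they are built on all patients who took the drug, every entry in the last two columns is zero.

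**The case against.** A reader might infer that SAEs and deaths in such patients disappear from the safety summaries. The documents do not support that as a flat statement. The SAP text that specifies the tables points to all treated subjects, SAP 9.2.3 applies no filter, and the listing shows every recorded event. Only the sentence in Protocol 12.2 leads to exclusion. Moreover, if all treated subjects is a wider set, the SAP tables lose nothing; if it is shorthand for the Safety Population, there is only one denominator. Both complaints cannot hold in full at once. This stands: what is shown is an unresolved conflict, not a loss.

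The baseline condition is also undefined. It may mean that every scale is finished, or only that the baseline visit took place; the list in Protocol 8.1.1 also includes instructions, system training and the dose itself. This stands too, but it does not remove the problem. It leaves membership of the safety set to later judgment.

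A second tempting inference is that the safety profile will look better than it is, because patients who cannot finish the scales are likely to be more impaired. That is plausible, since all disease stages and mild cognitive impairment are eligible. Against it, Exclusion Criterion 4 removes patients unlikely to complete the assessments reliably, and a Care Partner may record the patient's answers. The documents give no basis for the size of such a bias and do not establish its direction.

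Finally, safety is not the principal objective (Protocol 11.1), and SAEs must be reported whatever the analysis set. Both points lower the severity. Neither is a reason for a baseline condition in a safety set, and the documents state no benefit from having one.

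**Conclusion.** The point holds as a conflict of denominators built on an unsuitable membership condition. If Protocol 12.2 governs, an exposed patient with incomplete baseline assessments and any event in that patient are missing from the summary tables but present in the listing. If the wording of SAP section 9 governs and is read literally, nothing is lost. The documents do not settle which applies.

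The effect is probably small: about 5 to 27 of 540 patients under the assumed 1% to 5%, with 0.05 to 1.35 expected SAE patients at an assumed SAE rate of 1% to 5%. The primary analysis, which uses the Evaluable Population, is not affected. The correction should be made, but it is not critical to the study.

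**What to change.** - In Protocol 12.2 and SAP 6.5.2, define the Safety Population as all consented patients who received at least one dose of XADAGO. The consent condition stays, because event collection starts only once consent and the first dose are both in place.
- Name the Safety Population as the set for every table in SAP section 9, replacing references to all treated subjects and filling the gap in 9.2.3.
- Keep the baseline condition in the ITT definition (SAP 6.5.3), and restate it in the Evaluable definition (SAP 6.5.4 and Protocol 12.2), which would otherwise lose it.
- Point the Protocol 12.2 sensitivity analysis of the primary endpoint to the ITT population. ITT has the present Safety wording, so that analysis is unchanged. Protocol 12.2 lists only two populations, so the ITT definition must be added there.
- Add the ITT count to the disposition table in SAP 7.1, since the Safety and ITT sets would no longer be identical.

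**Cost.** Wording changes in both documents, with no new data and no change in sample size. The demographic and medical history tables (SAP 7.3 and 7.4) would include a few patients with incomplete baseline scales.

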### **6.5.3. ITT Population**

The ITT Population is defined as all subjects who sign informed consent for the study, complete baseline assessments, and receive at least 1 dose of XADAGO. ITT population will be used to analyze all efficacy endpoints except MDS-UPDRS.

#### **6.5.4. Evaluable Population**

The Evaluable population comprises all subjects in the safety population who complete at least the MDS-UPDRS assessment at the Study Day 60 visit. Evaluable population will be used to analyze MDS-UPDRS endpoint.

#### **6.6. Baseline Assessments**

Baseline assessments are defined as the last non-missing result prior to administration of the first dose of study medication. For continuous variable, if multiple measurements were done at the same date without time variable collected, baseline will be defined as the average of multiple measurements on the same date. For lab parameters, all lab results, including local and central lab ones, will be used to derive the baseline value.

#### **6.7. Derived and Transformed Data**

##### **6.7.1. Baseline Age**

Subject's age in years will be calculated based on date of informed consent date using the following formula:

$$\text{Age (year)} = \text{FLOOR}((\text{date of informed consent} - \text{date of birth})/365.25*12)$$

where FLOOR( ) function returns the integer part of the result.

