9. SELECTION AND WITHDRAWAL OF PATIENTS

9.1. Inclusion Criteria

1. Patient (and Care Partner if required per Inclusion 7) is able to understand and provide signed informed consent and HIPAA authorization in English
2. Diagnosis of idiopathic PD (all stages)
3. Male or female, 30 to 80 years of age, inclusive, at initial screening assessment
4. Independent of the study, clinician's and patient's choice of treatment is XADAGO in accordance with the Package Insert indication ([Appendix A](#))
5. Patient is willing and able to participate in the study and complete study-related assessments for 2 months and, patients can continue for an optional 4-month study extension
6. Patient has access to an electronic device for the interim completion of PROs
7. Patient has an available Care Partner who is able and willing to assist with clinic attendance and completion of study assessments (e.g., PROs, health outcomes, etc.), if in the PI's opinion, assistance is needed to comply with all study visits and procedures

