12.5. Subgroups and Covariate Adjustment

Age, sex, and disease duration will be included in any subgrouping and/or covariate modeling. When variables are used in modeling, the inclusion in model will only stay if the p-value < 0.10 for those situations.

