### **7.3. Demographic and Baseline Characteristics**

All subjects in the safety population are included in the post text table which summarizes the subject population, and for all treated subjects by cohort and overall, with respect to age at entry into the study, age at onset of the condition under study, sex, race, weight, height, body temperature, any primary diagnostic criteria and/or secondary co-morbid diagnoses.

Age will be reported in years and summarized with descriptive statistics N, mean, s.d., median, and range (e.g., minimum and maximum values), and as a frequency distribution in the groups of 30-<65 and >65 years.

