### **8.2. Subgroup Analyses**

No subgroup analyses will be done in this study.

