### **8.4. Analysis of the Efficacy Endpoint**

The change in MDS-UPDRS, PDQ-39, and MoCA from the Baseline Assessment Visit to the Primary Endpoint (Study Day 60) will be summarized by cohort and overall. An analysis of paired t-test will be used to analyze the continuous endpoints.

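### The SAP's age formula returns months although it is labelled years, and once that is corrected the two age bands leave out patients aged 65

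*SAP*

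**What the plan says.** SAP 6.7.1 (Baseline Age) says that "age in years will be calculated based on date of informed consent date using the following formula". It labels the result as age in years, and the formula is FLOOR((consent date − birth date)/365.25*12), where FLOOR takes the integer part.

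SAP 7.3 (Demographic and Baseline Characteristics) confirms the unit: "Age will be reported in years and summarized with descriptive statistics N, mean, s.d., median, and range". It also asks for age "as a frequency distribution in the groups of 30-<65 and >65 years".

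Protocol 9.1 sets the range that these rules must cover: "Male or female, 30 to 80 years of age, inclusive, at initial screening assessment".

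No other section gives a different age formula or assigns age 65 to a band.

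**The concern.** A difference between two dates in days, divided by 365.25, is already in years. The further factor of 12 converts it to months, which contradicts the text and the label in the same section as well as the reporting unit in SAP 7.3.

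The bands have a separate problem. Because FLOOR yields whole numbers, a corrected age can be exactly 65, and 65 is neither below 65 nor above it.

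At stake are the age rows of the demographics table: first the unit, then a frequency distribution that does not add up to N. Of the two, the band gap is the easier to miss. A mean age in the hundreds is noticed at once, whereas two percentages that sum to a little under 100 can pass as missing data.

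**Working it through.** **Inputs.** The formula is from SAP 6.7.1, the bands from SAP 7.3, and the eligible ages of 30 to 80 inclusive from Protocol 9.1 (so up to the day before the 81st birthday). Consent dates are taken from 1 November 2017 to 30 April 2020, the planned study period in the Protocol synopsis, as the widest possible range. The ceiling of 540 patients is from Protocol 8.2 and 12.3.

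**1. Does the formula return 30 to 80?** It does not.

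| True age at consent | Days (example) | Days/365.25*12 | Formula result over all consent dates |
|---|---|---|---|
| 30th birthday | 10,957 | 359.98 | 359 or 360 |
| 65th birthday | 23,741 | 779.99 | 779 or 780 |
| 80th birthday | 29,220 | 960.00 | 960 |
| Day before 81st birthday | – | – | at most 971 |

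The result is approximately months. It can be one lower than calendar completed months because 365.25 is an average year length.

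**2. Does another grouping of the terms give years?** Reading it as days/(365.25*12) gives 30/12 = 2.5, floored to 2, at the bottom, and just under 81/12 = 6.75, floored to 6, at the top. Neither reading yields years.

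**3. Effect on the bands as written.** A formula value below 65 requires a true age below 65/12 = 5.42 years. So 0% of eligible patients fall in 30-<65 and 100% fall in >65.

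**4. Bands after the factor 12 is removed.** Testing each whole number from 30 to 80 against the two bands, 65 is the only one that fits neither. Patients with that derived age still count in N, mean, SD, median and range, but appear in neither frequency row.

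**5. How many patients that could be.** The documents give no age distribution, so this is illustrative only.

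- Normal distribution truncated to ages 30 up to 81, with assumed mean 60 to 70 and SD 7 to 12: the share with 65 ≤ age < 66 runs from 3.1% (mean 60, SD 12) to 5.8% (mean 66, SD 7).
- Uniform over the 51 whole ages: 1/51 = 2.0%.
- At 540 patients: 540 × 1/51 = 10.6 up to 540 × 0.0577 = 31.2, so about 11 to 31, and proportionally fewer if fewer enrol.

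**6. Is deleting the factor 12 enough?** FLOOR(days/365.25) equals true completed years in 99.86% of 1,322,578 consent-date and birth-date pairs covering ages 30 to 80. The remaining 1,884 pairs (0.14%) are one year low, on or about a birthday; that is roughly 0.0014 × 540 = 0.8 patients. When consent falls exactly on a birthday the error is common: the result is 29 on 730 of 911 possible 30th-birthday dates, and 64 on 850 of 911 possible 65th-birthday dates.

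**The case against.** The strongest reply is that this is a self-revealing slip. The intended unit is stated twice in SAP 6.7.1 and again in SAP 7.3, and a mean age in the hundreds would not survive a first look at the table. No outcome analysis depends on it either: SAP 8.2 states "No subgroup analyses will be done in this study", and SAP 8.4 says "An analysis of paired t-test will be used to analyze the continuous endpoints", with no covariates. All of this stands, and it limits the importance of the point. It does not make the written rule correct, and it does not cover the band gap, which is much less conspicuous.

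The band gap could be a greater-than-or-equal sign lost when the PDF was read. That is possible, and the table shells that would settle it are not in the supplied text. The text as supplied reads >65, so the sponsor should at least confirm it.

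Protocol 12.5 says "Age, sex, and disease duration will be included in any subgrouping and/or covariate modeling", which might seem to carry the error further. For age as a linear covariate, however, months in place of years essentially rescales the coefficient and leaves its p-value nearly unchanged. Only banded subgrouping would be affected, and the SAP plans none.

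Lastly, completed birthdays are a refinement. Given the 99.86% agreement, deleting the factor 12 would be adequate for a descriptive table.

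**Conclusion.** Both defects hold on the text as written. The formula in SAP 6.7.1 returns approximately months (359 to 971 for eligible patients) under a label of years. After correction, the bands in SAP 7.3 omit a derived age of 65. The first result is exact arithmetic over the planned consent dates. The number of patients in the gap, about 11 to 31 of 540, rests entirely on assumed age distributions and on full enrolment. The consequence is confined to the descriptive age summaries. This should be corrected, but it does not threaten any conclusion about the study's outcomes.

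**What to change.** In SAP 6.7.1, define age as completed years, meaning birthdays reached by the date of informed consent. If a day-count formula is preferred, drop the factor 12 and accept that it can be one year low on or about a birthday, including a derived 29 for an eligible patient who consents on a 30th birthday.

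In SAP 7.3, use the bands 30-<65 and >=65 years, and check that the table shells mentioned in SAP 6.4 show the same bands.

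The two changes belong together, because correcting the unit is what brings the gap into effect. They should be made before database freeze, by which time SAP section 2 requires analysis decisions to be settled. The cost is two short text edits and one check of the demographics shell, with no change to data collection or to any outcome analysis.
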